HLA antibody prevalence in blood donors*	Percent of TRALI that are antibody mediated**	Average # components per transfusion episode***	'control' r	Number required in each of 'case' and 'control' recipients arms for different power estimates		
			80%	85%	90%	
8.5%	80%	6	806	917	1067	
9.0%	80%	6	886	1007	1175	
10.0%	80%	6	1034	1178	1379	

* Results for LAPS show the HLA prevalence to be about 16% for women and about 1% for men, hence overall prevalence of HLA antibodies in units transfused in hospitals participating in LAPS-II is likely to be in the range of 8.5% to 10%.

** Approximately 80% to 85% of TRALI cases are thought to be antibody mediated. The required sample size decreases as the immune mediated percentage increases, thus conservatively 80% is used in the table.

*** Recipients receiving an apheresis component are assumed to receive no other components during the transfusion episode. Recipients receiving an FFP (or other plasmas) component are assumed to receive on average a total of 6 components during the transfusion episode, and as a worst case scenario the additional components are assumed to be high risk TRALI components.

H4. Sample size and power selected for the study: From the above table and the details provided in Appendix D, the sample size selected was 1,175 for the antibody positive components and 1,175 for the antibody negative components. This number will give 90% power to detect a TRALI rate difference between the two groups of recipients. This conservatively assumes that a transfusion episode consists of 6 components although apheresis platelet component transfusion is most often a single unit transfusion episode. The percentage of TRALI that is antibody mediated is assumed to be 80% which may also be a conservative estimate. To the above number, a 10% margin is added to account for missing records etc. Therefore, the total number of antibody positive and antibody negative components is 1,295 for each group.

Based on OSMB recommendations we plan to conduct an interim analysis to see if the estimated sample size is adequate. The interim analysis will assess the average number of components per transfusion episode (assumed to be 6) and the TRALI incidence per component of unknown HLA status (assumed to be 0.18%). If the average is much greater than 6 or the incidence much lower than 0.18%, then increasing the sample size will be considered. A detailed description of the interim analysis is provided in Appendix H.

H5: Pilot study for record review: In collaboration with [name], [name] and her co-investigators, and REDS-II Working group for LAPS-II, a pilot study has been conceived and is being conducted as of this writing. The study will assess the feasibility of: (a) whether a non-physician can perform the medical record reviews, (b) the amount of time needed to retrieve the information, (c) the amount of time needed per chart review, and (d) the expert
(medical) panel's ability to diagnose TRALI from the extracted data collected during the chart review.

For the pilot, LAPS-II data collection forms were utilized by a research nurse (pilot nurse) working with [name] group. [name] is the Principal Investigator for the REDS-II site of Blood Centers of the Pacific/BSRI. This blood center is one of the five REDS-II Centers that will participate in LAPS-II. The pilot nurse was trained by the nursing staff working with [name] for the prospective TRALI study at the University of California at San Francisco (UCSF). The pilot nurse was given blood unit identifier (BUI) numbers from 20 plasma or plateletpheresis units transfused to 20 patients with the following diagnoses: 3 patients who were previously diagnosed as TRALI cases; 3 patients who were previously diagnosed as having had Acute Lung Injury (ALI) that did not meet the criteria for a diagnosis of TRALI; 3 patients who were diagnosed as Transfusion-associated cardiac overload (TACO); and 11 cases who did not have ALI, TACO, or TRALI. These cases were selected from the case files of [name] current prospective study. The pilot nurse was not informed about the type of cases she was reviewing. As far as was possible, FFP and plateletpheresis products were selected for the pilot.

As a part of the pilot, a time study was performed to assess the time needed to retrieve the information (retrieval time) for completing the data collection form for the blood bank information (e.g., patient demographic, date/time of product issue etc.). Time needed to perform exclusions (including completing the data collection forms) was measured for those cases in which TRALI wasn't a differential diagnosis. Finally, time required for the extended chart review, data collection, and the preparation of a narrative summary for those cases in which TRALI was a differential diagnosis was measured. In [name] on-going prospective study, the prospective study nurse prepares several PowerPoint slides to summarize such cases and the summary is then reviewed by the Expert Panel to classify cases as TRALI, not TRALI, ALI, TACO etc. For the pilot, the pilot nurse similarly prepared a summary for the cases in which TRALI was a differential diagnosis. These data are available to share with the record review coordinators for training. The results of the pilot demonstrated that the process to exclude the cases in which TRALI was not in the differential diagnosis was effective.

H6. Study population, enrollment, and human subject research: There are two types of study subjects in this protocol, namely, blood donors and transfusion recipients. Study donors are from the REDS-II supported Leukocyte Antibody Prevalence Study-I (LAPS-I). All these donors have been tested for HLA class I and HLA class II antibodies and some have been tested for neutrophil antibodies per the LAPS-I protocol. All HLA antibody positive donors at the five REDS Centers participating in LAPS-II will be eligible for the current study (and a proportion of HLA antibody negative donors will also be selected as controls). It should be noted that most will not been tested for neutrophil antibodies. Any TRALI cases in recipients will prompt testing of the donor's repository specimen for HNA antibodies (if not already tested). All donations made after the HLA antibody tested donation and donations made by these donors in the previous years from the time of antibody testing may be eligible for the study. Current estimates are that we would perform retrospective review of donations going back for a period of two years.

There is no risk to the study donors that will arise from this proposed research except that very few donors might be deferred from donating blood in the future if found to be implicated in TRALI; the possibility of such deferral is already included in the original LAPS-I informed consent. Also, donors with HLA antibodies but who are not implicated in TRALI may need to be diverted from apheresis platelet donation based on recent AABB recommendations; however, this outcome would result from donor participation in the original LAPS protocol and is not a consequence of this proposed protocol. Donor consent for proceeding with investigation of the recipients of their donations will be waived because such investigation falls within the expected transfusion medicine practice.

The study recipients of blood transfusion will be selected from participating hospitals and are those patients who have already received the study blood components from antibody positive and negative LAPS study donors. Transfusion recipient consent will be waived because: (a) this study involves record review of previously recorded clinical information and therefore poses minimal risk related to loss of confidential health information (b) all data will be managed in a confidential manner, in particular, the centralized database will not contain patient's name or the hospital's medical record number, (c) the access to recipient data will be restricted to authorized individuals, and (d) the study cannot be performed if the recipient consent is required because of the significant number of recipients who may have already expired after the transfusion due to the known high mortality rates after transfusion from their primary disease.

The recipient data will be linked and the linking would allow follow up of those transfusion recipients who are believed to have had TRALI discovered by the current research. For follow up, other blood components transfused within 6 hours of onset of TRALI will be identified and the donors of involved units will be investigated for leukocyte antibodies using a standardized investigation protocol. In case of any deaths identified by current research that are believed to be due to TRALI, the blood bank medical staff of the hospital will be notified for donor investigation and reporting the case to the FDA as per local hospital protocol. The only risk involved for the recipient is the possibility of loss of confidentiality of private health information. Safeguards will be taken to prevent the loss of confidentiality. Additionally, a certificate of confidentiality will be obtained (see below).

H6A. Certificate of confidentiality: A certificate of confidentiality from the National Institute of Health will be obtained. With this certificate, the researchers cannot be forced to disclose information that may identify the donor or the recipients even by a court subpoena, in any federal, state, or local civil, criminal, administrative, legislative, or other proceedings. The researchers will resist any demands for information from personnel of the United States Government that is used for auditing or evaluation of federally funded projects or for information that must be disclosed in order to meet the requirements of the federal Food and Drug Administration (FDA). Researchers do not plan to voluntarily disclose information obtained with this research.

I. Inclusion criteria

For blood donors, the inclusion criteria include those with HLA antibodies and some of the donors who do not have antibodies. Not all donors with HLA antibodies may be needed. Among

donors without HLA antibodies, the selection will be based on gender and parity frequencymatching at each REDS-II Center with the antibody positive donors.

For transfusion recipients, inclusion criteria will be all those recipients who received the study blood components at participating hospitals. Further record review will be conducted on those recipients who had a chest x-ray within 24 hours after the study transfusion.

J. Exclusion criteria

For blood donors from the LAPS, some donors without leukocyte antibodies will be excluded due to the fact that the number of antibody negative LAPS donors exceeds the numbers needed for this study.

K. Informed consent

Consent will be waived for blood donors since recipient investigation on blood donations from routine blood donors is a known part of general transfusion medicine practice. Also, there is no risk to the donors except for potential for loss of confidentiality of private health information. Safeguards will be in place to protect the confidentiality of the information. There will be a small risk that a donor who is not part of LAPS may be deferred from donating blood in the future if the donor is clearly implicated in a case of TRALI or is found to have antibodies upon recall testing. However, this risk is no different than if such a donor was found to be implicated or involved in a TRALI case that occurred outside of this study.

Informed consent from transfusion recipients is also waived because all recipient data will be obtained and maintained in a confidential manner and therefore the risk to the recipients is minimal from the loss of confidential private health information. The Centralized data will be maintained at Westat, the coordinating center for REDS-II research program. Westat has considerable experience in managing centralized database to ensure confidentiality of the donor and recipient data. All resulting publications will not contain recipient names or other personal identification information. The data will be linked to permit investigation of additional donors in those TRALI cases which are identified through the research and which were not previously reported to the blood bank. Potential for loss of confidentiality of private health information exists, but several safeguards will be in place to protect the information.

L. Data analysis

The primary analysis will compare the TRALI incidence among case recipients to the TRALI incidence among control recipients. Fisher's exact test for 2x2 tables will be used. The presumed statistical significance will imply HLA antibody in a transfused blood component is a risk factor for TRALI. Then secondary analysis will estimate;

- the probability of a HLA antibody-positive high risk component causing TRALI
- the probability of a HLA antibody-negative component causing TRALI
- the probability of a component of unknown HLA antibody status causing TRALI
- the proportion of TRALI due to HLA antibodies (i.e. immune-mediated)

Additional analyses will involve estimating TRALI incidences and other incidences. Analysis will be conducted to assess the incidence of TRALI and possible TRALI per unit transfused and per transfusion recipient. For this analysis the number of units transfused per episode per patient will be derived from the data available in the data collection forms. Incidence will also be calculated, when possible, for (a) TRALI without other risk factors and TRALI with other risk factors, (b) among those with other risk factors, incidence will be calculated for ALI which cannot be distinguished from TRALI and for ALI that is not TRALI but that occurred within 6 hours or >6 hours of transfusion.

Analysis of other incidences is described below. In addition to the transfusion complications described above, incidence for transfusion-associated cardiac overload will be based on cases that are classified by the Medical panel as TACO.

Using appropriate statistical methods, associations will be explored between different transfusion complications described above (TRALI, no-TRALI, possible TRALI, ALI of undetermined origin, TACO) and the underlying clinical information, such as, demographics, diagnosis (CPT codes), co-morbid conditions (e.g. renal failure), degree and severity of hypoxemia, chest x-ray and cardiac abnormalities. Data, when available, will be correlated with the presence of HLA and HNA antibodies (signal strength and/or specificity of antibodies) in the recipients as well as the involved donors and their HLA and HNA phenotypes to assess the antibody specificity and the corresponding cognate antigens in donor/recipient pairs among different groups of patients with complications described above. Frequencies of clinical symptoms of transfusion complications will be ascertained. Recipient outcome data, when available, will be tabulated for different types of transfusion complications. Clinical characteristics of the cases that were reported to the blood bank before the study and after the study will be compared.

M. Timeline

The protocol will be submitted to local IRBs (university/hospitals) for review and approval and also to each participating REDS-II Blood Center's IRB for review and approval. For some hospitals, the hospital's Medical Executive Committee or Privacy Board may review/approve the protocol as appropriate. The study protocol submitted to the hospital's IRBs (or Privacy Board) may include deployment of a certified honest broker. Also, record review coordinators for data collection will be subject to local hospital's requirements. Once IRB (Privacy Board) approvals have been received, blood centers can identify blood components needing record review at the hospitals and notify the hospitals. We expect that identification of components by the blood centers and hospital-based record review will be completed by April 2009. Anticipated start date for accruing patient data is October 2008. Data compilation, analysis, and reports are expected to be completed in six months.

Table-13: Time table

Item	Target Date
Finalize protocol & Forms	June 2008
Centers IRB submission and approval	June -July 2008
*Rolling IRB approvals of participating hospitals	June – Sep 2008
Obtain Certificate of Confidentiality	Aug – Sep 2008
Develop SOP	July – Sep 2008
Systems Development	June - Sep 2008
Nurse coordinator training at UCSF	Sep/Oct 2008
Blood center staff training (systems training)	Sep/Oct 2008
Data Collection	Dec 2008 – June 2009
*Perform Interim Analysis	March 2009
Data cleaning and coding	July 2009
Data analysis/reports	Aug - Oct 2009

* We envision obtaining "rolling IRB approvals". Submissions for IRB approval would be made in June 2008. Data collection would start with as many hospitals as we are able to obtain IRB approvals from. Interim analysis would be performed after 1/3 of the data is collected.

N. Budget

LAPS-II Blood Center Budget Guidelines

An itemized budget estimate along with justifications is presented below.

(a) Record review coordinator: \$91,000.00

Initial training 60 hours (50% effort for 3 weeks)
Coordinating by phone with each hospital, 30 minutes/day for 5 days per week for 24 weeks = 60 hours
On-site coordination of access to medical records includes waiting to have records pulled, 15 minutes/chart, 518 charts = 130 hours
Screening form completion: 30 minutes/per form X 518 forms = 259 hours
Data entry of the screening forms: 15 minutes/form x 518 forms = 130 hours
Detailed chart review: 3 hours/chart, 62 charts = 186 hours
Data transmission of the detailed forms to the Coordinating Center: 15 minutes/form for 62 forms = 16 hours
Preparation of PowerPoint slides, 1 hours/chart, 62 charts = 62 hours
+ Travel time for six months, one hour each day of the week for 5 days per week for 26 weeks = 130 hours

Subtotal hours = 1,033 hours

Add 40% additional time for unforeseen delays in getting access to medical records and increased numbers needed due to interim analysis= $1,033 \times 0.4 = 413$ hours

Total hours for record reviewer = 1,033 + 413 = 1,446.

0.7 FTE (based on 2080 hours/FTE).

*Salary = \$100,000/FTE X 0.7 FTE = \$70,000.00 + 30% fringe = \$91,000.00

+ Depending on geographic location of hospitals this could be more or less than one hour/day.

*Salary estimate based on ICU/Critical Care Nurse. It is likely that a Physician's Assistant or Respiratory Therapist with similar experience would have comparable salary requirements.

(b) REDS-II Blood Center Study Coordinator

It is expected that before the record review coordinator starts the review, the Study Coordinator will spend 25% of his/her time getting IRB approvals, training, organizing etc. for 6 months and then 10% for 6 months. However, this cost is already budgeted in the overall Center budget.

(c) **Donor services department associate:** \$4,333.00 (To prepare a list of components distributed to the participating hospitals)

One month effort at 40,000.00/year salary = 3,333.00 + 30% fringe = 4,333.00. This individual will prepare a list of blood components donated by the LAPSI study donors for the index donation, all subsequent donations, and all donations in previous two years. This individual will prepare a list of the components from these that are distributed to the participating hospitals. The goal is to identify 518 components from the antibody positive donors and 518 components from the antibody negative donors. The total number of components to be studied is 518.

Total for donor services department associate = one month effort at 40,000.00/year = 33,333.00 + 30% fringe = 4,333.00

(d) **Blood bank labor:** \$6.00/product = \$3,108.00

Blood bank to retrieve the information regarding which recipient received the product and the time of issue, etc. Ten minutes per product. Total products per center = $518 = 518 \times 10.0 = 5,180.00 \text{ minutes} = 86 \text{ hours} = 86/2080 = 0.04 \text{ FTE}.$

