H2. Hospital participation rate: Assuming that the participating hospitals receive about 50% of blood components distributed by the REDS-II centers, a total of 2,590 blood components will be evaluated from antibody-positive donors and 2,590 blood components from antibody-negative donations. The number of components donated by the LAPS donors that would allow the total number of components (2,590 in each group) needed for the study is described in section F8 above.

H3. Assumptions underlying power considerations: We have assumed that about half of the donations are given by male donors and half by female donors with about 17% of the latter having HLA antibodies. We also assumed that 1% of male donors are HLA antibody positive. Thus, we assumed that about 9% of components received by a recipient on average are HLA antibody-positive. These numbers are supported by the recently analyzed data from LAPS-I in which 17.2% of female donors were HLA antibody positive as compared to 1% of male donors. They are further supported by three published studies. First, the study of 324 apheresis female donors showed a prevalence of HLA class I & II antibodies of 16.7% (Densmore 1999). Second, a study of 1416 UK blood donors (males and females) showed a prevalence of HLA class I & II antibodies (Bray et al. 2004). The results from the LAPS study indicate the prevalence will be about 9% in all (males plus females) donors.

We also further assumed that there will be only one study component transfused per patient and that there will not be new onset hypoxemia in any given patient more than once during the transfusion episode involving the study component.

Another assumption for the power calculation is that 80% of the TRALI cases result from leukocyte antibodies. This assumption is supported by the original studies of [name] reported in 1985. More recent data also support this assumption. For instance, antigen-antibody correspondence was demonstrated in 87% (13 of 15) of cases in one recent series (Kopko et al. 2002). An analysis of fatal TRALI cases reported to FDA also has demonstrated the presence of donor leukocyte antibodies in 83% (40 of 48) of the cases. (Holness L et al.).

Based on these assumptions and data from the study by Finlay et al., we estimate

- the probability of a HLA antibody-positive high risk component causing TRALI to be 1.59%
- the probability of a HLA antibody-negative component causing TRALI to be 0.04%

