For each HLA positive donor in the study, we consider all of this donor's components in the study period, and enroll recipients of these components as case subjects. In our case recipient group, we will know that one component is HLA positive and that any other components (the number of other components can vary for each recipient) the recipient receives have unknown HLA status. For each HLA negative donor in the study, we consider all of this donor's components in the study period, and enroll recipients of these components as control subjects. In our control group, we will know that one component is HLA negative and that any other components the recipient receives have unknown HLA status. Assume the number of components a recipient receives can be anything from 1 to 11, and averages 6. (Of minor note, the case and control groups will have a higher mean number of components than the overall recipient mean. The reason is that recipients with greater number of components have a higher chance of selection into the study, i.e. since we select components and find the recipient that

received that component, then a recipient with 11 components has 11 chances to be selected, while the recipient with a single component has just 1 chance to be selected).

Using the estimates of TRALI incidence per component (conditional on whether a component is HLA positive, HLA negative, or unknown HLA status), we can estimate the TRALI incidence per case recipient and per control recipient by first calculating the probability of not developing TRALI when receiving on average of 6 components (range 1-11), and then taking the complement of that probability to estimate the probability of the recipient developing TRALI after receiving these components. As an example, a case recipient who receives one HLA antibody-positive high risk component and two high risk components whose HLA status is unknown would have a probability of not developing TRALI equal to $(0.0159) \times (0.0018) \times (0.0018)$ and a probability of developing TRALI equal to $1-\{(0.01.59) \times (0.0018) \times (0.0018)\}$. Using this method, we estimated that the TRALI rates would be about 2.32% for case recipients and 0.79% for control recipients.

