The estimate of 0.79% for control recipients is close to the Finlay estimate (0.85%=7/820) as expected. The Finlay estimate is the TRALI incidence for recipients transfused with components of unknown HLA status. Knowing that one of the transfused components is HLA negative lowers the risk slightly, while the greater average number of components in the control group raises the risk slightly, for a net negligible change in the risk. The estimate of 2.32% in case recipients is less than the composite estimate for other lookback studies (2.7%=5/184). This too is expected, as the other lookback studies only considered components from donors who had been 'implicated' in a TRALI incident.

If the average number of transfused components per recipient were 4 rather than 6, then the TRALI rate estimates in the case recipient group and control recipients groups are lowered to 2.0% per case recipient and 0.5% per control recipient. The statistical power of the study increases as average number of components decreases. Conversely, the statistical power of the study decreases as the average number of components increases. If the interim analysis finds the average to be larger than 6, then increasing the sample size will be considered (see Appendix H). A one-sided 0.05 level test with samples of 1,175 in each of the two recipient groups will have 90% power to statistically detect a greater TRALI incidence among case recipients if 6 components are transfused (statistical power computed using StatXact for an exact conditional test comparing two binomial proportions).

Appendix E: Expected participating hospitals for LAPS-II: IRB, type of medical records, and difficulty in accessing records

No.	No. Participating Hospital Name		Type of IRB (check one)			Patient records (Check one)		On a scale of 1-5 how easy is it to obtain access to medical records?				
							Very easy			Very difficult		
		Hosp	Univ	Other	Electro- nic	Paper	1	2	3	4	5	
		Но	xwort	h Bloo	d Center			1				
1	University Hospital		X		Х		X					
2	Christ Hospital	Х			Х			Х				
3	Jewish Hospital	X			Х			х				
4	Good Samaritan	X			Х			х				
	Hospital											
	The	e Institu	ite for	Transf	fusion Me	edicine						
5	UPMC Presbyterian		Х		Х			Х				
6	UPMC Shadyside		Х		Х			х				
7	Children's Hospital of Pittsburgh of UPMC		X			Х			Х			
8	UPMC Passavant		х			х			Х			
9	UPMC St. Margaret		х		х				Х			
10	Magee-Women's Hospital of UPMC		X		Х				Х			
11	UPMC McKeesport		Х			Х			Х			

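### The 90% power at 1,175 per arm already assumes single-unit apheresis episodes; with 6 components for every recipient, as H4 and Appendix D describe it, power is about 82–87%

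*Protocol*

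**What the plan says.** The protocol describes the number of components per transfusion episode in two ways.

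- **H3 and the Table-12 footnote.** H3 assumes six components per plasma episode and one unit per plateletpheresis episode, and gives a 70/30 split of study components between plasma and apheresis platelets. The footnote repeats this: "Recipients receiving an apheresis component are assumed to receive no other components during the transfusion episode". Only plasma recipients average 6.
- **H4.** Directly below that table, H4 selects 1,175 per arm for 90% power and adds: "This conservatively assumes that a transfusion episode consists of 6 components although apheresis platelet component transfusion is most often a single unit transfusion episode". Its interim check uses an assumed average of 6 per episode, with no split by component type.
- **Appendix D.** The derivation says "Assume the number of components a recipient receives can be anything from 1 to 11, and averages 6" and notes that recipients of more components are more likely to be selected. It concludes that 1,175 per arm "will have 90% power to statistically detect a greater TRALI incidence among case recipients if 6 components are transfused". It mentions neither the 70/30 mix nor the apheresis exception.

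**The concern.** The word 'although' in H4 makes sense only if 6 components were also applied to apheresis recipients, so that single-unit episodes would be a bonus. If single-unit apheresis is already inside the calculation, that bonus has been used.

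The direction matters. Zero other components is the most favourable value an apheresis recipient can have, and H3 and H4 support it only as the usual case, not for everyone. Each further component adds the same background risk in both arms and dilutes the contrast. On this one input a reader of H4 would think power can only exceed 90%, when departures can only lower it.

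The same confusion carries into the interim check. If the sizing used a blended average below 6, an observed overall average of 6 would look on plan when it is not.

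**Working it through.** **Inputs.** Per-component risks from H3: "the probability of a HLA antibody-positive high risk component causing TRALI to be 1.59"%, 0.04% for an HLA-negative component and 0.18% for one of unknown status. All further components are treated as high risk (Table-12 footnote). The mix is 70% plasma and 30% apheresis (H3). Design, from Appendix D: "A one-sided 0.05 level test with samples of 1,175 in each of the two recipient groups will have 90% power", with "statistical power computed using StatXact for an exact conditional test comparing two binomial proportions".

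**Step 1: reproduce the stated figure.** Appendix D: "we estimated that the TRALI rates would be about 2.32% for case recipients and 0.79% for control recipients". Enumerating both binomials with the one-sided 0.05 exact conditional test gives power 90.0% at 1,175 per arm. The numbers required for 80/85/90% are 886, 1,007 and 1,175, exactly the 9.0% row of Table-12.

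**Step 2: what the stated rates imply.** Recipient risk = 1 − (1 − p)·Q. Here p is the risk of the known component and Q is the mean of (1 − 0.0018)^(k−1) over the component count k.

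- Control: Q = 0.9921/0.9996, so further components = ln Q / ln 0.9982 = 4.18.
- Case: Q = 0.9768/0.9841, which gives 4.13.

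An average of 6 for everyone means 5 further components, or more with size-biased selection. So 6 for all does not produce 2.32% and 0.79%.

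**Step 3: rebuild the rates under each reading.** The protocol does not give the shape of the 1–11 distribution. I assumed a symmetric triangular shape with mean 6, weighted by component count as Appendix D describes (mean 6.97).

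- That distribution for every recipient: 2.64% vs 1.11%.
- The same for the 70% plasma recipients, one component for the 30% apheresis recipients:
  - case: 0.7 × 2.642 + 0.3 × 1.59 = 2.33%
  - control: 0.7 × 1.109 + 0.3 × 0.04 = 0.79%

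The mixed build recovers the protocol's rates, with power 90.3%.

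**Step 4: power at 1,175 per arm with 6 components for every recipient.**

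| Component count | Case | Control | Power |
|---|---|---|---|
| 1–11 uniform, size-biased | 2.76% | 1.23% | 81.5% |
| 1–11 triangular, size-biased | 2.64% | 1.11% | 83.9% |
| 1–11 binomial, size-biased | 2.55% | 1.01% | 85.9% |
| Flat 6, no size bias | 2.47% | 0.94% | 87.4% |

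Removing the 30% single-unit share directly from the stated 2.32% and 0.79%, with no shape assumed, gives 2.63% vs 1.11% and power 83.4%.

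**Step 5: partial departures.** In the triangular build, if apheresis recipients average 1, 2, 3 or 5 further high-risk components, power is about 89%, 88%, 87% or 85%.

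**Step 6: the average used for sizing.** 0.7 × 6 + 0.3 × 1 = 4.5. With size bias, 0.7 × 6.97 + 0.3 × 1 = 5.2. Both are below the interim benchmark of 6.

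**The case against.** The strongest reply is that no number is wrong and nothing is hidden. The 1,175 reproduces exactly, and the single-unit assumption is stated in H3 and again in the footnote immediately above H4. That stands: this is a contradiction in how the 90% is described, not an error in the sample size.

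Second, a reader might infer that the design has no conservatism left and that power must fall below 90%. The documents do not support that. H3 expects 3–4 components per episode and takes six for plasma, and the footnote treats every further component as high risk. With the triangular build:

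- 4 components for all recipients gives 92.1%.
- 6 for all, with further components in the mix of the reference hospital study in Appendix D (51% low risk at one-sixth the risk), gives an average risk of 0.18% × (0.49 + 0.51/6) = 0.10% each and power of 92.7%.
- If the extras in apheresis episodes are red cells at one-sixth risk, 5 of them leave power at 89.4%.

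These cushions are real. They do not make the apheresis assumption conservative.

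Third, a reader might infer that 90% requires every apheresis recipient to be single-unit. That holds approximately in the size-biased build that reproduces the protocol's rates. With a flat 6 for plasma, a single-unit share of about 15% is enough.

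Fourth, Appendix H re-runs the H4 sizing with the observed component distribution, which could correct the apheresis input. That softens the interim point. But the H4 trigger is still a single average of 6, and neither H4 nor Appendix H says that the two episode types are to be assessed separately.

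**Conclusion.** The point holds as a contradiction about the condition attached to the 90%. H4 and the Appendix D power sentence attach it to 6 components for recipients generally, while H3, the Table-12 footnote and the stated rates show that it assumes single-unit apheresis for 30% of recipients. On the wording of H4 and Appendix D, power is about 82–87%: about 84% for the shape that reproduces the protocol's rates and 87% for a flat 6. The range rests on the protocol's own per-component risks, all further components being high risk, and a component distribution the protocol does not specify, so no single figure within it should be quoted as the true power.

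It does not follow that 1,175 is too small or that the study is underpowered. The interim benchmark of 6 should nevertheless change, because an overall average of 6 already exceeds the 4.5 (about 5.2 with size bias) on which the sizing rests.

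**What to change.** 1. In H4 and the Appendix D power sentence, state the condition in full: 1,175 per arm gives 90% power if plasma recipients average 6 components and apheresis recipients receive no other component; if all recipients average 6, power is about 82–87%.
2. In H4, stop describing the apheresis part as conservative. Keep the word for six components in plasma episodes and for treating further components as high risk.
3. Replace the single interim benchmark of 6 with two, plasma episodes (6) and apheresis episodes (1), and use both observed values in the Appendix H recalculation.

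The cost is a few sentences and a split tabulation at the interim. No extra patients are needed, and the stated power becomes less favourable.
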